##### **Analyses of primary and secondary efficacy endpoints:**

Analyses of primary and secondary efficacy endpoints will be based on the ITT population, with missing values imputed using last observation carried forward (LOCF) imputation (whereby the last value is considered as the value of threshold sensitivity at entry/screening DBPCFC). Because threshold sensitivity to peanut protein for all randomized subjects will be  $\leq 300$  mg (based on the exclusion criteria), subjects who discontinue prior to the post-treatment DBPCFC will be counted as non-responders in the efficacy analyses.

In addition, primary and secondary efficacy analyses will be repeated on the FAS.

Besides, the robustness of the primary and secondary efficacy analyses conclusions will be explored via sensitivity analyses on the PP population (thus excluding subjects who discontinue from the study prior to the post-treatment DBPCFC or those with a major protocol deviation that impacts the primary efficacy criteria).

Lastly, sensitivity analyses of the primary efficacy endpoint will be conducted on the overall ITT population using multiple imputation and worst-case imputation (which means subjects from the Viaskin® Peanut group who discontinue prior to the post-treatment DBPCFC will be counted as non-responders and subjects from the placebo group who discontinue prior to the post-treatment DBPCFC will be counted as responders) instead of the LOCF imputation to assess the robustness of the primary efficacy analyses with regards to handling of missing data.

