### 8.5.1.2 *Statistical Methods*

The primary efficacy analysis will be performed on the ITT population (that is on all randomized subjects), using LOCF imputation (which means that subjects with missing DBPCFC value at Month 12 will be considered as non-responders). An exact logistic regression will be used to compare the percentage of treatment responders at Month 12 in the active Viaskin® Peanut 250 µg group versus the placebo group, adjusting for screening ED stratum and including the treatment group as fixed effect. A 2-sided, 1% significance level will be used to test the null hypothesis. The corresponding p-value as well as the number and percentage (95% confidence intervals [CIs]) of responders will be presented by treatment group. The difference between active and placebo response rates and the corresponding 95% CI will be presented. The clinical relevance of the treatment effect will be evaluated based on the lower bound of the 95% CI being higher or equal to 15%. This 15% difference is intended to exhibit a clear robustness of the treatment effect.

Relative risks of achieving response in the active group compared to the placebo group will be assessed using a log-binomial regression with the screening ED stratum and treatment group as covariates and will be presented together with associated 95% CI.

The study will be considered positive, if the p-value from the exact logistic regression is significant ( $p < 0.01$ ) and the lower bound of the 95% CI of the difference between active treatment and placebo response rates is higher or equal to 15%.

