### 8.10 Determination of Sample Size

The objective of this study is to assess the efficacy and safety of Viaskin® Peanut to induce desensitization to peanut in peanut-allergic children after a 12-month treatment period of EPIT. This will be evaluated by assessing the percentage of treatment responders in the active Viaskin® Peanut 250 µg group compared to the placebo group.

The sample size is calculated based on the following assumptions:

- A 40% response rate for the active Viaskin® Peanut 250 µg group and 10% response rate for the placebo group in the overall population, with a 2-sided type-I error rate  $\alpha$  set to 1%;
- A lower bound of the 95% CI of the difference between active treatment and placebo response rates  $\geq 15\%$  in the overall population and  $>0\%$  in each stratum;
- A 60% response rate for the active Viaskin® Peanut 250 µg group and 10% response rate for the placebo group in Stratum 1, with a 2-sided type-I error rate  $\alpha$  set to 5%;

- A 30% response rate for the active Viaskin® Peanut 250 µg group and 10% response rate for the placebo group in Stratum 2, with a 2-sided type-I error rate  $\alpha$  set to 5% and a power (1- $\beta$ ) set to 85%;
- The following expected distribution of the screening ED strata:
  - 1/3 of children having a screening ED from 1 mg to 10 mg;
  - 2/3 of children having a screening ED from 30 mg to 300 mg.
- A ratio 2:1 to maximize the number of subjects treated in the active Viaskin® Peanut 250 µg group.

Therefore, the sample size calculated for Stratum 2 is 185 subjects (approximately 123 subjects in the active Viaskin® Peanut 250 µg group and 62 subjects in the placebo group). Hence, if 185 children with a screening ED from 30 mg to 300 mg are required in the study, then, according to the expected distribution of the screening ED strata, approximately 95 children having a screening ED from 1 mg to 10 mg should be randomized, resulting in a total of 280 subjects evaluable for the primary efficacy endpoint in the analysis.

This number of subjects leads to a power of 99% in the overall population and in the Stratum 1.

This is summarized in Table 10.

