**Table 10: Summary of Sample Size Calculation**

Population	alpha	Power	Sample size (N=N1+N2) Expected Response Rate			Lower bound of the 95% CI of the difference
			Viaskin ® Peanut 250 µg	Placebo	Total	
Screening ED Stratum 1	5%	99%	N1=63 60%	N2=32 10%	N=95	>0%
Screening ED Stratum 2	5%	85%	N1=123 30%	N2=62 10%	N=185	>0%
Overall population	1%	99%	N1=186 40%	N2=94 10%	N=280	≥15%

Abbreviations: CI = Confidence interval; ED = Eliciting dose; N = Number of subjects.

To allow for a potential premature withdrawal rate of about 15%, the study will randomize a total of 330 subjects: 220 subjects will be randomized to receive Viaskin® Peanut 250 µg and 110 subjects to placebo. Among the 330 subjects randomized, a minimum of 20 subjects will be randomized for each of the following ages: 4 years, 5 years and 11 years, respectively. Besides, a minimum number of 75 children of either 4 or 5 years of age must be randomized.

The distribution per ED stratum should lead to approximately 110 subjects with a screening ED from 1 mg to 10 mg and approximately 220 subjects with a screening ED from 30 mg to 300 mg, provided that the same distribution as obtained in the Phase IIb VIPES study is reproduced. If this expected distribution is not fully respected during the recruitment in the PEPITES study, a minimum of 50 subjects would need to be included in Stratum 1 in order to guarantee a power of  $\geq 90\%$  in this stratum and at least

220 subjects would need to be included in Stratum 2 in order to guarantee a power of  $\geq 85\%$  in this stratum.

From experience, the screen failure rate could be up to 30%; hence, up to 470 peanut allergic subjects might need to be screened.

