#### 4.8.1.5 Examination of Subgroups

The treatment effect for the primary efficacy variable will be examined as secondary efficacy analyses in each of the subgroup defined according to the screening ED. Sample size has been calculated to demonstrate a treatment difference at the level of 5% in each of the screening ED stratum based on a lower bound of the 2-sided Newcombe 95% CI of the difference between active treatment and placebo response rates  $>0\%$ :

- At a power of 99% in stratum 1, with an expected response rate of 60% in the active treatment vs. 10% for placebo, both estimated using missing=failure method
- At a power of 95% in stratum 2, with an expected response rate of 30% in the active treatment vs. 10% for placebo, both estimated using missing=failure method.

To handle cases of randomization stratum error (i.e. the stratum recorded in the IWRS was not consistent with the actual screening ED value), screening ED subgroups were considered for secondary analyses using the actual screening ED value (i.e. subjects will be considered in the screening ED subgroup corresponding to the actual screening ED value).

The treatment effect for the primary efficacy variable will also be examined as secondary

CCI

CONFIDENTIAL

Project Document Version No. 3.0

Project Document Effective Date: 04-Oct-2017

Page 35 of 79

efficacy analyses in each of the following age groups: 4-5 year of age, 6-11 year of age (respectively [4-6[, [6-12[).

Response rates by treatment groups and treatment effect will also be provided descriptively, as exploratory analysis, for each region and on the following subgroups:

- Gender (Male/Female)
- Race (White/Black or African American/Asian/Other)
- Subjects with / without history of asthma
- Subjects with / without history of allergy other than peanut
- Subjects with / without history of atopic dermatitis or eczema.

Analysis will be performed only on subgroups containing at least 15 subjects.

According to the sample size of each subgroup (if  $N < 50$ ), exact 2-sided 95% CIs will be provided instead of 2-sided Newcombe 95% CIs for the difference in response rates. In the presence of sparse data (i.e. at least one of the percentages is zero) the following will not be presented:

- within-treatment confidence intervals around response rate (of 0%),
- between-treatment comparative p-value.

A forest plot will be provided summarizing the primary efficacy variable in the above subgroups.

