### Main analysis

The primary efficacy endpoint is the difference between percentage of treatment responders in the active Viaskin® Peanut 250 µg group compared to the placebo group after 12 months of EPIT treatment. A subject is defined as a treatment responder if:

- The initial ED was  $\leq 10$  mg peanut protein (Screening ED subgroup 1) and the ED is  $\geq 300$  mg peanut protein at the Month 12 DBPCFC; or
- The initial ED was  $> 10$  mg peanut protein (Screening ED subgroup 2) and the ED is  $\geq 1,000$  mg peanut protein at the Month 12 DBPCFC.

The primary efficacy analysis will be performed on the ITT population, using missing=failure imputation method (which means that subjects with missing DBPCFC peanut eliciting dose value at M12 will be considered as non-responders).

The primary measure of treatment effect will be the difference in response rates between active and placebo treatment groups. The primary analysis will apply a Wald test at a 2-sided 5% significance level to evaluate a null hypothesis of no difference, and the corresponding 2-sided Newcombe 95% confidence interval (CI) for the difference in response rates will be calculated. The clinical relevance criterion for the primary analysis will be defined by a  $\geq 15\%$  lower confidence bound, and this condition will determine whether the primary objective has been successfully met.

The Wald test p-value will be calculated using the SAS® GENMOD procedure, with DIST=binomial and LINK=identity option of the MODEL statement.

The 2-sided Wilson 95% CIs of individual response rate will be presented overall and by treatment group using the SAS® FREQ procedure, with the RISKDIFF option.

All methods described above will be performed using SAS® procedures described in [Appendix 2: SAS® Code lines](#)

The study will be considered positive if the lower bound of the 95% CI of the difference between active treatment and placebo response rates is higher or equal to 15%. This 15% difference is intended to exhibit a clear robustness of the treatment effect.

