#### 4.12 Determination of Sample Size

The sample size is calculated based on the following assumptions:

- A 40% response rate for the active Viaskin® Peanut 250 µg group and 10% response rate for the placebo group, both estimated under “Missing=failure” method (based on a maximum drop-out rate of 15%) in the overall population;
- A lower bound of the 95% CI of the difference between active treatment and placebo response rates  $\geq 15\%$  in the overall population and  $>0\%$  in each screening ED stratum;
- A 60% response rate for the active Viaskin® Peanut 250 µg group and 10% response rate for the placebo group in screening ED Stratum 1, both estimated under “Missing=failure” method (based on a maximum drop-out rate of 15%);
- A 30% response rate for the active Viaskin® Peanut 250 µg group and 10% response rate for the placebo group in screening ED Stratum 2, both estimated under “Missing=failure” method (based on a maximum drop-out rate of 15%);
- The following expected distribution of the screening ED strata:
  - o 1/3 of children having a screening ED from 1 mg to 10 mg;

- o 2/3 of children having a screening ED from 30 mg to 300 mg.
- A ratio 2:1 to maximize the number of subjects treated in the active Viaskin® Peanut 250 µg group.

Therefore, the overall sample size calculated is approximately 330 subjects evaluable for the primary efficacy endpoint in the analysis (220 subjects in the active Viaskin® Peanut 250 µg group and 110 subjects in the placebo group). Hence, according to the expected distribution of the screening ED strata, approximately 110 children having a screening ED from 1 mg to 10 mg and 220 children having a screening ED from 30 mg to 300 mg should be randomized.

This number of subjects leads to a power of >90% in the overall population, >99% in the Stratum 1 and >95% in the Stratum 2.

This is summarized in the following Table.

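### The protocol's 99% overall power is that of the p<0.01 test only; the lower bound of at least 15%, which decides success, has about 83–87% on the protocol's own numbers, and SAP 4.13 does not record the later change to 90%

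*Protocol*

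**What the plan says.** **Protocol.** Section 8.10 and the synopsis list, for the overall population, response rates of 40% v 10% with a two-sided alpha of 1%, and also a 95% CI lower bound for the difference of at least 15%. The calculation starts from Stratum 2, "resulting in a total of 280 subjects evaluable for the primary efficacy endpoint in the analysis", and 8.10 then says "This number of subjects leads to a power of 99% in the overall population and in the Stratum 1". The overall row of Table 10 holds alpha 1%, power 99%, 186 v 94, 40% v 10% and the bound of at least 15%. Below the table: "To allow for a potential premature withdrawal rate of about 15%, the study will randomize a total of 330 subjects".

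Section 8.5.1.2 gives the success rule: "The study will be considered positive, if the p-value from the exact logistic regression is significant" at p<0.01 and the lower bound is at least 15%. The primary analysis covers all randomized subjects. Section 8.2.2.4 adds that "subjects who discontinue prior to the post-treatment DBPCFC will be counted as non-responders in the efficacy analyses".

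**SAP.** Section 4.8.2 drops the p-value from the rule: "The study will be considered positive if the lower bound of the 95% CI" is at least 15%, with a Newcombe interval. Section 4.12 says "Therefore, the overall sample size calculated is approximately 330 subjects evaluable for the primary efficacy endpoint in the analysis" (220 v 110). It gives 90% power for the bound in the table and more than 90% in the text. The assumed rates are defined as already counting missing as failure; 4.8.1.5 says the same for Stratum 2: "with an expected response rate of 30% in the active treatment vs. 10% for placebo, both estimated using missing=failure method". Section 4.13, which lists changes from the protocol, has no entry on power or its basis.

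**The concern.** A power figure printed beside a success criterion reads as the power to meet that criterion. In the two stratum rows this is true: the stated power holds for both the test and the bound. In the overall row it is not. A difference of 30 points is far from zero but only 15 points above the required bound, so the bound is much harder to meet than p<0.01. A reader who takes the 99% at face value would put the risk of missing the pivotal criterion at about 1% under the design assumptions. The two documents also give 99% and 90% for the same bound without explaining why.

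**Working it through.** **Inputs.** 186 v 94, 40% v 10%, alpha 1% two-sided, bound of at least 15% (protocol 8.10, Table 10, 8.5.1.2); 220 v 110 with the same rates and a Newcombe 95% CI (SAP 4.12, 4.8.2). The protocol names no CI method for the difference, so both Newcombe and Wald are shown.

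**Step 1: reproduce the 99%.** Test of zero difference at 1%:
- pooled rate = (186×0.40 + 94×0.10)/280 = 83.8/280 = 0.2993
- SE under the null = √[0.2993×0.7007×(1/186 + 1/94)] = 0.0580
- SE under the alternative = √(0.24/186 + 0.09/94) = 0.0474
- power = Φ[(0.30 − 2.576×0.0580)/0.0474] = Φ(3.18) = 99.9%

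Fisher's exact test at 1%, enumerated, also gives 99.9%. The stated figure reproduces for this test.

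**Step 2: the bound at 280.** By normal approximation, power = Φ[(0.30 − 0.15)/0.0474 − 1.96] = Φ(1.20) = 88.6%. The exact figure sums the binomial probabilities of all outcomes whose lower bound is at least 0.15:

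| Analyzed | Newcombe | Wald | Stated |
|---|---|---|---|
| 186 v 94 | 83.1% | 87.1% | 99% (protocol) |
| 220 v 110 | 89.2% | 91.8% | 90% in table, more than 90% in text (SAP) |

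As an illustration, with 9/94 placebo responders (9.6%) the bound needs at least 65/186 (34.9%) active responders by Newcombe, where the lower limit is 15.4%, or 63/186 (33.9%) by Wald, where it is 15.3%.

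**Step 3: the joint rule.** No possible 2×2 table at 186 v 94 meets either bound and has Fisher p≥0.01, so requiring p<0.01 as well costs nothing. With the response rates set by stratum (63 at 60%, 123 at 30%, placebo 10%) and an exact test stratified by screening ED, simulation gives 99.95% for p<0.01 alone. The joint rule has 84.4% (Newcombe) and 88.2% (Wald), the same as the bound alone.

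**Step 4: the stratum rows.** For a bound above zero by Newcombe, Stratum 1 (63 v 32, 60% v 10%) has 99.96% and Stratum 2 (123 v 62, 30% v 10%) has 90.2%; Fisher's test at 5% gives 99.9% and 88.0%. Both meet the protocol's 99% and 85%. At the SAP's 146 v 74, Stratum 2 has 94.6% by Newcombe, in line with 95% after rounding.

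**Step 5: the basis.** The protocol applies its rates to 280 evaluable subjects and then inflates for withdrawal, 280/0.85 = 329, rounded to 330. Its primary analysis nevertheless keeps all 330 and counts withdrawals as non-responders. The SAP applies the same rates to 330 and defines them as missing=failure. The number randomized and analyzed is 330 in both; only the basis of the power calculation differs.

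**The case against.** The strongest reply is that 99% sits beside alpha 1% and is correct for that test, with the bound a separate column and a separate assumption. The bound might even be read as the value expected at the assumed rates, which is 19.7% (Newcombe) or 20.7% (Wald) and exceeds 15%. This explains where the number came from. But nothing in 8.10 or the tables limits the 99% to the test, and 8.5.1.2 requires both conditions.

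A second reply is that 83–87% describes 280 subjects, a set the primary analysis does not use, and that the SAP already gives 90% for exactly this rule. Both points are right, and they limit the practical size of the problem. They do not withdraw the 99% from the protocol or supply the missing entry in SAP 4.13.

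Three stronger readings are tempting, and the documents do not support them:
- **An undeclared increase in sample size from 280 to 330.** Both documents randomize 330 and analyze all of them.
- **A trial that is too small.** For 99% on the 15% rule, about 579 (Newcombe) or 549 (Wald) subjects would have to be analyzed, but neither document needs 99% for that rule, and about 90% is an ordinary target.
- **True power of only 65–71%.** That follows if 40% and 10% are completer rates diluted by 15% drop-out in each arm (34% v 8.5% at 220 v 110). The protocol's inflation step invites this reading, but the SAP says that the rates already count missing as failure.

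**Conclusion.** The point stands as a misstated power figure and a gap in the record of changes. On the protocol's own row, the chance of missing the bound is 13–17% (100 − 87.1 to 100 − 83.1), against the 1% that the row suggests. On the set actually analyzed, with the SAP's definition of the rates, it is 8–11%. These figures assume true rates of 40% and 10%; the range in each reflects the choice between Wald and Newcombe limits. The SAP's 90% in the table is about right, and its claim of more than 90% in the text is slightly high for Newcombe (89.2%). The Stratum 1 and Stratum 2 rows of Table 10 are sound. Severity is low to moderate: the SAP already carries a near-correct overall figure, and no sample size, test or decision rule is affected.

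**What to change.** 1. **Protocol synopsis, 8.10 and Table 10.** Label 99% as the power of the p<0.01 test only. State the power of the 15% rule once and on one basis, preferably about 89–90% at 330 with the rates defined as missing=failure, as in the SAP. On that basis, drop the wording about 280 evaluable subjects plus 15% inflation from the ITT power statement, because withdrawals are then already inside the rates.
2. **SAP 4.12.** Change the text figure for the overall population from more than 90% to about 89–90%.
3. **SAP 4.13.** Add an entry that the basis of the power calculation changed: from 280 evaluable to 330 ITT with missing=failure, overall power from 99% to 90%, and Stratum 2 power from 85% to 95%. Say that the numbers randomized and analyzed did not change.

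The cost is a few lines of text and a less favourable stated power.

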**Table 10: Summary of Sample Size Calculation**

Population	alpha	Power	Sample size (N=N1+N2) Expected Response Rate			Lower bound of the 95% CI of the difference
			Viaskin ® Peanut 250 µg	Placebo	Total	
Screening ED Stratum 1	5%	99%	N1=63 60%	N2=32 10%	N=95	>0%
Screening ED Stratum 2	5%	85%	N1=123 30%	N2=62 10%	N=185	>0%
Overall population	1%	99%	N1=186 40%	N2=94 10%	N=280	≥15%

Abbreviations: CI = Confidence interval; ED = Eliciting dose; N = Number of subjects.

To allow for a potential premature withdrawal rate of about 15%, the study will randomize a total of 330 subjects: 220 subjects will be randomized to receive Viaskin® Peanut 250 µg and 110 subjects to placebo. Among the 330 subjects randomized, a minimum of 20 subjects will be randomized for each of the following ages: 4 years, 5 years and 11 years, respectively. Besides, a minimum number of 75 children of either 4 or 5 years of age must be randomized.

The distribution per ED stratum should lead to approximately 110 subjects with a screening ED from 1 mg to 10 mg and approximately 220 subjects with a screening ED from 30 mg to 300 mg, provided that the same distribution as obtained in the Phase IIb VIPES study is reproduced. If this expected distribution is not fully respected during the recruitment in the PEPITES study, a minimum of 50 subjects would need to be included in Stratum 1 in order to guarantee a power of  $\geq 90\%$  in this stratum and at least

220 subjects would need to be included in Stratum 2 in order to guarantee a power of  $\geq 85\%$  in this stratum.

From experience, the screen failure rate could be up to 30%; hence, up to 470 peanut allergic subjects might need to be screened.

## 9 ETHICAL, LEGAL, AND ADMINISTRATIVE ASPECTS

### 9.1 Data Quality Assurance

The Sponsor or Sponsor's designee will conduct a site visit or a site phone contact to verify the qualifications of each Investigator, inspect the site facilities, and inform the Investigator of responsibilities and the procedures for ensuring adequate and correct documentation.

The Investigator is required to prepare and maintain adequate and accurate case histories designed to record all observations and other data pertinent to the study for each study participant. All information recorded in the e-CRF for this study must be consistent with the subjects' source documentation (that is medical records).

